1.4.2 Other Endpoint(s)

Other endpoints will be evaluated at the specific follow-up time points may include, but not limited to, mitral regurgitation severity, New York Heart Association (NYHA) class, LV function and anatomy, cardiac medication, adverse events and device deficiency. Rate of heart failure hospitalizations in the 1-year post-procedure will be compared to the 1 year period prior to the index procedure.

Statistical Analysis Plan

1.4.3 Exploratory Endpoint(s)

The primary endpoints will be compared between the first 250 registered patients to the second 250 registered patients (or a 2-year registration period, whichever comes first), in order to evaluate the learning curve of the MitraClip procedure.

2.0 ANALYSIS CONSIDERATIONS

2.1 Analysis Populations

2.1.1 Intent-to-Treat Population (ITT)

All patients registered in the surveillance with MitraClip treatment attempted will be included.

2.2 Statistical Methods

Descriptive analysis will be performed to summarize baseline, procedural, clinical and safety event data. Depending on the type of data (e.g., continuous or categorical), statistical methods described in the section below will be used.

2.2.1 Descriptive Statistics for Continuous Variables

For continuous variables, such as age, results will be summarized as number of observations, means and standard deviations, and where applicable, with quartiles, minimums, maximums, and 95% confidence intervals for the means. Differences between the two groups, where specified, will be summarized with the differences of the two means, and 95% confidence intervals for the difference between the means.

2.2.2 Descriptive Statistics for Categorical Variables

For binary variables (e.g. SLDA rate, gender, diabetic status, etc.), results will be summarized with patient counts and percentages/rates, and where applicable, with exact 95% Clopper-Pearson confidence intervals. Differences between the two groups, when specified, will be summarized with the difference in percent and the Newcombe³ score 95% confidence interval for the difference of two percentages.

2.2.3 Survival Analyses

Survival analysis will be conducted using the Kaplan-Meier method. Patients without events will be censored at their last known event-free time point. Patients who withdraw will be censored at the date of withdrawal. Survival curves will be constructed using Kaplan-Meier estimates. Summary tables for endpoints will include event (failure) rates, Greenwood standard error and confidence interval for the event rates.

Statistical Analysis Plan

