3. SURVEILLANCE PERIOD

Information will be collected for up to 3 years post procedure. The target registration period will be from the date that patient registration is allowed upon execution of study agreement with each site to the last patient registered into the PMS. Shown below are specific details associated with the surveillance period.

- Approximate preparation period: 6 months
- Registration period: the estimate of the registration period for the PMS is about 2 years
- Follow-up period: 3 years
- Final re-examination report: 6 months
- Total PMS period: Approximately 6 years

Primary analysis data will be collected until all patients complete 30 days follow-up. Annual progress reports (up to 3 years) will be submitted to the regulatory authority at each time point accordingly.

Data will be collected at the following time points:

- Baseline (pre-procedure)
- Procedure
- Discharge
- 30 days (30 days+14 days) (by visit)
- 1 year (365 days±28 days) (by visit)
- 2 years (730 days±28 days) (by visit)
- 3 years (1095 days±28 days) (by visit)

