5.5 Scheduled Follow-up

Scheduled follow-ups include 30-day, 1-, 2- and 3-year post procedure. Record the following information at each follow-up time point:

- Type of contact (visit)
- Date of contact
- TTE
- NYHA class
- Adverse event occurred or change in symptoms from previous follow-up
- Changes on cardiac medications (started/changed/stopped)
- Device Deficiency

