5.7 Unscheduled Follow-up (only in case of reportable adverse event)

Complete Adverse Event form.

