2.4 Interim Analysis

No formal interim analyses are planned for this study. As such, no formal statistical rule for early termination of the trial is defined. Interim study reports with descriptive analysis may be produced for regulatory or reimbursement purposes.

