2.5 Timing of Analysis

Analyses for the primary endpoints will be performed when the last registered patient completes 30-day follow-up. Annual progress reports (up to 3 years) will be submitted to the regulatory authority at each time point accordingly.

Data will be collected at the following time points:

- Baseline (pre-procedure)
- Procedure
- Discharge
- 30 days (30 days±14 days) (by visit)
- 1 year (365 days±28 days) (by visit)
- 2 years (730 days±28 days) (by visit)

Statistical Analysis Plan

- 3 years (1095 days \pm 28 days) (by visit)

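### Censoring at the last event-free contact can inflate Kaplan-Meier rates in annual or interim reports cut between visits

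*SAP*

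**What the plan says.** **Censoring.** SAP 2.2.3 gives two rules: "Patients without events will be censored at their last known event-free time point" and "Patients who withdraw will be censored at the date of withdrawal". It does not define the first time point further, and it gives no rule for a data cut. Protocol 7.3 names all-cause mortality as an example of data for Kaplan-Meier analysis.

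**Contact.** Protocol 5.5 states: "Scheduled follow-ups include 30-day, 1-, 2- and 3-year post procedure". The windows in Protocol 3 include "30 days (30 days+14 days) (by visit" and "1 year (365 days±28 days) (by visit". SAP 2.5 gives the first window as "30 days (30 days±14 days) (by visit"; its lower end differs from the protocol, but both end at day 44. Protocol 5.7 is headed "Unscheduled Follow-up (only in case of reportable adverse event". Protocol 5.9 makes heart failure events and all other serious events, including fatal ones, reportable.

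**Reports before follow-up is complete.** SAP 2.5 places the primary-endpoint analyses after the last patient's 30-day follow-up and provides for annual progress reports to the authority. SAP 2.4 adds: "Interim study reports with descriptive analysis may be produced for regulatory or reimbursement purposes".

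**The concern.** A patient who dies on day 200 generates a report between visits. A patient alive on day 200 generates none, and is last known to be alive at the 30-day visit, between day 30 and day 44. At a data cut on that day, the rule in SAP 2.2.3 counts the death at day 200 and removes the survivor by day 44. Length of follow-up then depends on having had the event, which Kaplan-Meier estimation does not allow for. The estimate is too high, and the Greenwood interval is centred on the wrong value.

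At stake are mortality and other time-to-event rates in early reports to the authority or for reimbursement. The error fades as visits are completed, so rates could appear to fall from one report to the next for no clinical reason.

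**Working it through.** **Inputs from the documents**
- 30-day visit, latest day: 30 + 14 = 44.
- 1-year visit: 365 − 28 = 337 to 365 + 28 = 393. The gap without scheduled contact is up to 337 − 44 = 293 days.
- Registration lasts about 2 years (730 days). A patient is registered at femoral vein puncture (Protocol 2.2), so registration and procedure fall on the same day.
- Illustrative cut: 730 + 44 = day 774 after the first registration.

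**Assumptions, not in the documents**
- Uniform entry, constant hazard, all visits attended.
- 500 patients (two cohorts of 250, from SAP 1.4.3). With 250 patients the result is much the same (19.5%).
- 1-year mortality of 5% to 25%. The plan states no mortality and no Kaplan-Meier figure, so there is none to reproduce.

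**Hand check at true 15%**

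Daily hazard λ = −ln(0.85)/365 = 0.000445. Potential follow-up at the cut is uniform from 44 to 774 days. Consider day u between 44 and 365, among patients who would be alive at u:
- Deaths at u come from everyone whose potential follow-up reaches u, a share of (774 − u)/730.
- Survivors remain at risk only if their 1-year visit has taken place (taken here at day 365), a share of (774 − 365)/730 = 0.560.
- Patients not yet at 1 year are at risk at u only if they die before the cut, a share of a(u) = [(365 − u) − (1 − exp(−λ(365 − u)))/λ]/730.

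The hazard is therefore multiplied by r(u) = [(774 − u)/730] / [0.560 + a(u)]:

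| u | numerator | denominator | r(u) |
|---|---|---|---|
| 44 | 1.000 | 0.560 + 0.030 | 1.694 |
| 204.5 | 0.780 | 0.560 + 0.008 | 1.374 |
| 365 | 0.560 | 0.560 | 1.000 |

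Simpson's rule over 321 days: (321/6)(1.694 + 4 × 1.374 + 1.000) = 438. The cumulative hazard is λ(44 + 438) = 0.2146, and 1 − exp(−0.2146) = 19.3%, against a true 15%.

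**Simulation with the full visit windows**

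This comes out slightly higher than the hand check, because some 1-year visits fall before day 365 and those patients leave the risk set early.

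1-year estimate, cut at day 774, events known at once:

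| True | Present rule |
|---|---|
| 5% | 6.9% |
| 10% | 13.1% |
| 15% | 19.8% |
| 20% | 25.9% |
| 25% | 31.9% |

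Sensitivity at true 15%, day 774:

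| Setting | 1-year estimate |
|---|---|
| 30-day reporting lag | about 19% |
| 90-day reporting lag | about 17% |
| Half of survivors confirmed alive at the cut | 16.9% |
| All survivors confirmed at the cut | 15.0% |
| Events learned only at visits | 15.0% to 15.1% |

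If registration took from 1 to 2.5 years, with the cut 44 days after the last entry, the estimate would run from about 44% down to 18%.

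**Other cuts and horizons at true 15% 1-year mortality**
- 30-day estimate at day 774: 1.3%, true 1.3%.
- 1-year estimate once all 1-year windows have closed (730 + 393 = day 1123): 15.2%.
- 2-year estimate at that same cut, with 2-year visits incomplete: about 33%, true 27.8%.
- 3-year estimate at the final cut: 38.8%, true 38.6%.

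**The case against.** The strongest reply is that no planned report is shown to contain a biased estimate.

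- **Primary analysis.** A reader might infer that the analysis at about day 774 will report inflated 1-year mortality. The documents do not support this. SAP 2.5 plans that analysis for SLDA and APS, and SAP 2.3.1 analyses both as proportions with exact intervals. Day 774 serves here only as an example of an early cut.
- **Annual reports.** They are due at each time point, which can mean each calendar year or after each completed follow-up visit. On the second reading the bias is negligible.
- **Interim reports.** They are optional and descriptive, and no horizon is named. A reader might infer extreme inflation at, say, 180 days in a report cut after one year of registration. No such estimate is planned; the time points after discharge are 30 days and 1, 2 and 3 years.
- **Reporting speed.** Prompt reporting is inferred from Protocol 5.7 and 5.9, which say what is recorded, not when. Protocol 5.5 also collects adverse events at scheduled visits. The visible text gives no deadline, and one may stand in text that was removed.
- **Contact between visits.** A non-fatal reportable event also shows that the patient was alive. With an assumed 0.5 such contacts per patient-year, the day-774 figure falls to 19.0%, or 18.0% with a 30-day lag. The SAP wording would also allow a site's later knowledge of survival to count.

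These points stand and limit the finding. They do not remove it: the visible text requires neither confirmation of status at a cut nor a cut aligned with visits, and early reports with time-to-event summaries are permitted.

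**Conclusion.** The concern holds conditionally, at low severity. Two conditions are needed: a report shows a Kaplan-Meier rate at a horizon whose visit window is still open for some patients, and events reach the database between visits. The bias is then upward. In the worked case it is about 5 percentage points on a true 15% with immediate reporting, 4 with a 30-day lag and 2 with a 90-day lag. It is nil if events are learned only at visits or if every survivor's status is confirmed at the cut. These sizes rest on assumed mortality, uniform 2-year entry and full visit attendance.

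A reader might conclude that the surveillance will overstate mortality in general. It will not: both primary endpoints and estimates made after the visits for the horizon are complete are essentially unaffected. No hypothesis test or stopping rule depends on the early rates.

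**What to change.** Add to SAP 2.2.3: in any report cut before all patients have passed the visit window for time t, the Kaplan-Meier estimate at t uses only patients registered at least t + 28 days before the cut (t + 14 days for the 30-day visit). No estimate at t is shown if too few patients qualify; the SAP should state that minimum number.

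An equivalent rule counts events and follow-up only to the last visit whose window has closed. At day 774 it gives 14.0% at day 336, against a true 1 − exp(−0.000445 × 336) = 13.9%. It needs the same minimum number.

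A third option is to have sites confirm status at each cut and to censor survivors there. It also removes the bias, but adds work for the sites.

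The first rule needs one sentence and a date filter, and no new data. At day 774 it gives 15.3% against a true 15%. It keeps (774 − 393)/730 = 52% of registered patients, but the excluded patients contribute almost no survivor time near t, so little precision is lost: the standard deviation of the estimate is 2.2 to 2.3 percentage points under either rule.

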2.2.4 Recurrent Event Analysis

For recurrent event data such as recurrent heart failure hospitalization at 1-year pre- and 1-year post index procedure, data will be analyzed using a generalized estimating equation model (GEE), such as Poisson regression model.

To fit the GEE model, the input dataset will be prepared to include total hospital count and total follow-up time (in days) pre- and post-index procedure for each patient along with the indicator for the time cutoff. Summary tables for recurrent event endpoints will include number of patients with recurrent event, total number of events, event rate per patient-year, and confidence interval for the event rate.

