2. SURVEILLANCE METHOD

2.1 Patients

Based on the Ministerial Ordinance on Good Post-marketing Study Practice for Medical Device, the Surveillance will **consecutively register** patients with moderate to severe and severe mitral regurgitation (3+ and 4+ MR) in whom a MitraClip implant was attempted (Marketing Approval No. 22900BZX00358000, October 31, 2017, hereinafter referred to as “MitraClip”). Patients registered in the AVJ-514 clinical trial who received additional MitraClip procedures will be excluded from the Surveillance.

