6.2 Other Endpoints

Other endpoints will be evaluated at the specific follow-up timepoints per typical mitral regurgitation intervention clinical studies, including but not limited to, mitral regurgitation severity score, NYHA class, LV function and anatomy, cardiac medication, adverse events, device deficiency. Rate of heart failure hospitalizations in the 1 year post-procedure will be compared to the 1 year prior to the index procedure.

7. Statistical Analysis

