7.3 Statistical Analyses

No pre-specified hypothesis tests are planned for this surveillance. Descriptive analysis will be performed to summarize baseline, procedural, clinical and safety event data. Depending on the type of data (e.g., continuous or categorical), statistical methods described in this section below will be used.

For continuous variables such as age, results will be summarized with the numbers of observations, means, standard deviations, and 95% confidence intervals for the mean. These calculations will be done under the assumption that the data are approximately normal in distribution.

For time to event data such as all-cause mortality, Kaplan-Meier analyses will be used.

For recurrent event data such as recurrent heart failure hospitalizations post-procedure, data will be analyzed using a generalized linear model, such as Poisson regression model.

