1.3 Clinical Investigation Design

AVJ 17-519 is a prospective, multi-center, single-arm surveillance study of patients with moderate to severe and severe mitral regurgitation (3+ and 4+ MR) in whom a MitraClip implant was attempted (Marketing Approval No. 22900BZX00358000, October 31, 2017, hereinafter referred to as “MitraClip”). Information will be collected for up to 3 years post procedure.

- Approximate preparation period: 6 months
- Registration period: Approximately 2 years
- Follow-up period: 3 years
- Final re-examination report: 6 months
- Total PMS period: Approximately 6 years

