2.9 Adjustments for Covariates

Unless otherwise specified, no adjustments for covariates will be made for any of the variables in the analyses.

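### Heart failure admissions after the procedure are compared with the whole year before it, with no check on the run-up, so the ratio can fall below 1 without any device effect

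*SAP*

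**What the plan says.** - Protocol 6.2 sets the comparison: "Rate of heart failure hospitalizations in the 1 year post-procedure will be compared to the 1 year prior to the index procedure". SAP 1.4.2 repeats it: the post-procedure rate "will be compared to the 1 year period prior to the index procedure". Both list it under other endpoints, not primary ones.
- SAP 2.2.4 gives the analysis of "recurrent heart failure hospitalization at 1-year pre- and 1-year post index procedure": a GEE model such as Poisson regression. The input holds "total hospital count and total follow-up time (in days) pre- and post-index procedure for each patient", plus an indicator separating the two periods.
- SAP 1.3 describes a "prospective, multi-center, single-arm surveillance study", so there is no concurrent control.
- Protocol 2.1 defines entry as "patients with moderate to severe and severe mitral regurgitation (3+ and 4+ MR) in whom a MitraClip implant was attempted". A previous HF admission is not required.
- SAP 2.9 says that, unless otherwise specified, "no adjustments for covariates will be made for any of the variables in the analyses".
- Protocol 7.3 says: "No pre-specified hypothesis tests are planned for this surveillance".

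Neither document gives an expected HF admission rate, the share of patients treated after an admission, or the usual delay from admission to procedure. No interval before the procedure is left out, and no sensitivity analysis of the run-up is planned. The baseline list in Protocol 5.1 has no item for earlier HF admissions. SAP 3.1 lists HF hospitalisation in the prior year as a baseline variable, without saying whether dates are held.

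**The concern.** The pre-year ends on a date that clinicians choose. If some procedures are scheduled because the patient was recently admitted with HF, those patients carry at least one admission in the pre-year by selection. Nothing places a matching admission in the post-year. The pre-year rate then overstates the patient's underlying rate, and the ratio falls below 1 even if the device does nothing. Correct counting of the index stay, and of follow-up time in patients who die, does not remove this, because the excess comes from earlier, separate admissions.

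One total per patient and period, as the model input is described, cannot show whether admissions cluster before the procedure. The before/after ratio is the plan's named comparison on HF admissions, and SAP 2.4 allows descriptive reports for regulatory or reimbursement purposes. A ratio well below 1 with a narrow interval could be read there as benefit even though no test is attached.

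**Working it through.** The plan states no figure for this comparison, so there is none to reproduce. All values of lambda (underlying HF admissions per patient-year), f (share of patients treated soon after a triggering admission), between-patient spread and delay are assumptions.

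**1. Closed form, no device effect.** With one added triggering admission in a share f of patients:

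pre-year rate = lambda + f; post-year rate = lambda; ratio = lambda/(lambda + f).

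| lambda | f = 0 | f = 0.2 | f = 0.3 | f = 0.5 |
|---|---|---|---|---|
| 0.4 | 1.00 | 0.4/0.6 = 0.67 | 0.4/0.7 = 0.57 | 0.4/0.9 = 0.44 |
| 1.0 | 1.00 | 1.0/1.2 = 0.83 | 1.0/1.3 = 0.77 | 1.0/1.5 = 0.67 |

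The range over f = 0.2 to 0.5 is 0.44 to 0.83. If the trigger is added only for patients with no other admission in the last 90 days (gamma frailty variance 0.5 to 1.0), the range is 0.47 to 0.86.

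**2. Simulation, no device effect.** Gamma-Poisson patient rates with dispersion 1, triggers 14 to 90 days before the procedure, and patients with higher rates more likely to be triggered. The full-year ratios are:

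| lambda | f = 0 | f = 0.10 | f = 0.25 | f = 0.50 |
|---|---|---|---|---|
| 0.25 | 1.00 | 0.73 | 0.55 | 0.43 |
| 0.5 | 1.00 | 0.84 | 0.72 | 0.60 |
| 1.0 | 1.00 | 0.92 | 0.83 | 0.75 |

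The chance that a 95% interval (paired rate ratio, robust variance) lies wholly below 1, across the three values of lambda, is:

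| N | f = 0 | f = 0.10 | f = 0.25 |
|---|---|---|---|
| 500 | about 3% | 32-80% | 93-100% |
| 250 | about 3% | 19-51% | 66-99% |

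N = 500 is taken from the two groups of 250 in SAP 1.4.3. The target in Protocol 2.3 is not legible in the public text.

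**3. Forces in the other direction.** If the natural rate would rise 30% in the second year, the null ratio for lambda 0.5 is 1.30, 1.10, 0.93 and 0.78 at f = 0, 0.10, 0.25 and 0.50.

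**4. Leaving out part of the run-up.** In the simulation, dropping the last 90 days returns the ratio to 0.99-1.00. That follows by construction, because every trigger was placed inside those 90 days. It does not show that 90 days is the right window. Dropping only 30 days barely helps: for lambda 0.5 and f 0.25 the ratio moves from 0.72 to 0.75.

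The exclusion can also mislead. Suppose the rate steps up 1.5-fold in the last 90 days, the rise would have persisted, and the true device ratio is 0.7. With the earlier rate set to 1:

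- Post-year rate = 1.5 x 0.7 = 1.05.
- Full pre-year rate = (275 x 1 + 90 x 1.5)/365 = 410/365 = 1.123, so the ratio is 1.05/1.123 = 0.93.
- Pre-period limited to days -365 to -91: rate 1, so the ratio is 1.05.

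Both ratios then understate the benefit, and the exclusion ratio does so more.

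**The case against.** The strongest reply is that the mechanism is not in the documents. Entry is by severity of regurgitation and an attempted implant. No passage says that an HF admission prompts referral, and with f = 0 the artefact is nil. A reader might infer that the planned comparison will show a reduction through regression to the mean. The documents do not support that: the size rests wholly on assumed values, and the direction is uncertain. Worsening disease pushes the ratio up, and so does the fact that patients must survive the pre-year, which therefore holds no fatal admissions. This part of the reply stands. What remains is that the planned model input could not tell f = 0 from f = 0.5.

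A reader might also infer that a pre-procedure peak could never be seen in this study. That goes too far. SAP 2.2.4 describes the model's input and not everything collected, and the case report form is not among the documents. Whether admission dates are held is unknown.

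Finally, this is a descriptive endpoint with no planned test, in a surveillance concerned mainly with safety, and the plan nowhere attributes a change to the device. That limits the weight of the point. It does not make the ratio interpretable when it is reported.

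**Conclusion.** The point holds as a possibility that the plan leaves unchecked. The full-year ratio is uncontrolled, and it can fall below 1 with no device effect if some procedures follow a triggering admission. Under the closed form the null ratio is 0.44 to 0.83 for lambda 0.4 to 1.0 per year and f 0.2 to 0.5, and 1.00 at f = 0. In the simulation, f = 0.10 was already enough to put the interval wholly below 1 in 32-80% of null studies of 500 patients. These figures assume a constant underlying rate; natural worsening can mask or reverse the effect.

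The evidence does not show that an observed reduction would be an artefact, or that a 90-day exclusion would give the true ratio. The two primary endpoints, single leaflet device attachment at 30 days and acute procedural success, are unaffected. The change is worth making because it is cheap and turns an assumption into something observed.

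**What to change.** 1. Record the date of each HF admission in the 365 days before the procedure, adding the item to Protocol 5.1 if the case report form does not already hold it.
2. In SAP 2.2.4, pre-specify a table of HF admission rates by quarter (or month) for both years.
3. In SAP 2.2.4, pre-specify a sensitivity analysis beside the full-year GEE ratio: the same model with the pre-period limited to days -365 to -91 and the exposure offset shortened to match.
4. State in Protocol 6.2 that the full-year ratio is uncontrolled and is not by itself evidence of a device effect.

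The cost is one date field per earlier admission, one refit, one table and one sentence. The sensitivity interval will be slightly wider, since it uses 275 pre-procedure days instead of 365. The exclusion analysis is biased against the device if the rise before the procedure is lasting worsening. It should therefore be read as a bound beside the full-year ratio, not as a replacement, and the two ratios need not bracket the true effect. If the quarterly rates show no rise before the procedure, the two ratios should agree closely and the concern falls away.
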